3.1.1. Analysis of primary outcomes

The difference in gestational weeks at birth will be evaluated using a linear effects model accounting for confounders of preterm birth, as measured at baseline. We estimate that about 57 out of 12,344 deliveries are for a second pregnancy for participants included in the sample given that 0.464% of participants who downloaded the app had two deliveries in the sample. We have included these women in the sample because we cannot exclude similar women in the usual care cohort given limitations in our data. Likewise, we cannot account for random effects of multiple deliveries using a mixed effects model.

Baseline study variables will be included as confounders in the model if (a) the literature has identified the variable as a confounder of preterm birth risk and (b) they might plausibly have influenced participants' decision to download the app. If, for a variable, the evidence on condition (a) is inconclusive and condition (b) is possible, we will examine the data and include the variable if it passes a 10% change-in-estimates threshold for the outcome or for the likelihood of downloading the app. The change-in-estimate will be calculated by adding each study variable to the model from the literature individually. Only baseline variables will be evaluated as potential confounders, as they could not have been affected by use of the app.

We will report the results of two models for each outcome, one using only confounders identified in the literature and one adding confounders identified empirically (Appendix A). Including fewer confounders will reduce the likelihood that the average treatment effect applies only to an unrepresentative subset of the population. Including additional confounders will reduce the likelihood of statistical bias in estimating the average treatment effect.

The dataset contains many known confounders of preterm birth that could be included in the model including:

- Previous preterm birth (3)
- Race (3)
- Low body-mass index (3,4)
- Insurance type (5)
- Area deprivation index (6)
- Multiple gestations (3)
- Previous spontaneous abortions (7)
- Hypertension (3)
- Diabetes (3)
- Tobacco use (3)

There are also many known predictors of preterm birth that are not in the EHRs, hence not available for this study. They include educational attainment, marital status, interpregnancy interval, relatives who delivered preterm, and genetic predictors of preterm birth (3).

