Some collected covariates are specific to this dataset. One is hospital location, which may capture differences in resources, practices, and patient populations. The second is the date of the first visit recorded in Epic, which may capture factors like access to care or social conditions (e.g., the pandemic). We will include hospital location as a variable in all models. We will not include date of first visit as it might be correlated with ones that affect the effectiveness of the app over time.

Residual plots will be used to evaluate the models for heteroskedasticity and the need for using robust standard errors, in order to allow for violations in the assumption that observations are independent and identically distributed (8).

Differences between the cohorts will be described using adjusted mean differences and p-values. Results will be considered significant at $p < 0.05$.

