3.1.5. Additional statistical considerations

Method for handling confounding by indication

Because this trial is observational, there may be incomplete overlap in covariates between the MHP and usual care cohorts. To account for this possibility, inverse probability of treatment weighting will be used. Propensity score matching of comparable subgroups will also be used and reported as a sensitivity analysis (13).

Propensity score matching works by creating samples of participants who have the same likelihood of receiving treatment. Logistic regression will be used to generate propensity scores; nearest-neighbor matching without replacement will be used for matching. Baseline confounders will be included in the propensity score model, if they are related to the likelihood of receiving treatment and the outcome. Date of first visit will not be included in the model (for reasons given in Section 3.1.1). Participants without similar propensity scores, defined as greater than a caliper width, will be excluded from this sensitivity analysis. The average treatment effect will be calculated for the included subset of similar participants.

Austin recommends a “caliper width,” defined as the difference between two propensity scores, as “equal to 0.2 of the standard deviation of the logit of the propensity score”(14). To balance the internal and external validity of this sensitivity analysis, this caliper width will be used, unless it excludes more than 20% of the sample. In that case, the caliper width will be increased until 80% of the participants are included. If this is adjustment is needed, the results using the smaller caliper width will be reported in the supplemental material. Following Austin (2011), standardized differences, QQ-plots, box plots, cumulative distribution functions, and empirical nonparametric density plots will be used to check the differences in baseline covariates between the treated and untreated samples (13).

Time-effects

For the primary models, we have chosen not to include the first appointment date as it could capture factors that affect the effectiveness of the app. During the study time frame, many outside factors could have affected the outcomes, especially due to the COVID-19 pandemic.

Because of this we will conduct a sensitivity analysis including a time effect, the date of the participant's first prenatal visit, in each model.

4. Software

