PREGSTART_O_ANYHTN	Pre-existing hypertension in any of these forms or combinations, complicating pregnancy: essential hypertension, hypertensive heart disease, hypertensive chronic kidney disease, secondary hypertension, or unspecified hypertension. Diagnosed or listed as active problem at first prenatal visit. (binary variable);	Baseline covariate
PREGSTART_O_CARDIOMYOPATHY	Disease of the circulatory system affecting any stage of pregnancy. Diagnosed or listed as active problem at first prenatal visit. (binary variable); Definition came from EPIC codes	Baseline covariate
PREGSTART_O_GDM	Gestational diabetes mellitus. Diagnosed or listed as active problem at first prenatal visit. (binary variable)	Baseline covariate
PREGSTART_MEDREPORTED	Medications reported at first prenatal visit (binary variable)	Baseline covariate
PREVIOUS_GDM	Previous GDM in a prior pregnancy, not including this current pregnancy (gestational diabetes) (binary variable)	Baseline covariate
PREVIOUS_OBANYHTN	Previous gestational hypertension in a prior pregnancy, not including this current pregnancy (binary variable)	Baseline covariate

PREVIOUS_PREECLAMPSIA	Previous preeclampsia in a prior pregnancy (binary variable)	Baseline covariate
AUTOIMMDX_PT20WKS	Previous gestational autoimmune disease prior to 20 weeks (in prior pregnancy) (binary variable)	Baseline covariate
PRIOR_SBBTW16AND34	Prior stillborn between 16 and 34 weeks in a prior pregnancy (binary variable)	Baseline covariate
PRIOR_LBBTW31AND36	Prior premature live birth between 31 and 36 weeks in a prior pregnancy (binary variable)	Baseline covariate
PRIOR_SBAFTER34	Prior stillborn after 34 weeks in a prior pregnancy (binary variable)	Baseline covariate
PRIOR_VPTBBTW222AND30	Prior very premature birth between 22 and 30 weeks in a prior pregnancy (binary variable)	Baseline covariate
PRIOR_STILLBORN	Prior stillborn (time period not specified) in a prior pregnancy (binary variable)	Baseline covariate
PRIOR_PPROM	Prior preterm premature rupture of membranes in a prior pregnancy (binary variable)	Baseline covariate
PRIOR_PPROMBEFORE37	Prior preterm premature rupture of membranes before 37 weeks in a prior pregnancy (binary variable)	Baseline covariate
HOSPITAL	which hospital they delivered at	Baseline covariate
SINGLETONS	1=singleton birth, 0=twins, triplets, etc (binary variable)	Baseline covariate
PREG_CONTACT_DATE	First visit in Epic while pregnant	Baseline covariate

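### The hospital covariate required in all models is the hospital of delivery, labelled baseline though fixed after app exposure and at the outcome event, and no adjusted model is clearly planned without it

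*SAP*

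**What the plan says.** Section 3.1.1 of the SAP introduces hospital location as a covariate specific to this dataset, "which may capture differences in resources, practices, and patient populations". It then sets the rule: "We will include hospital location as a variable in all models".

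Appendix A lists one hospital variable, HOSPITAL, described as "which hospital they delivered at" and typed as a baseline covariate. The two HOSP_ROLLUP fields hold payor data. No booking, prescribing or prenatal-care site is listed. The first visit appears only as a date, PREG_CONTACT_DATE ("First visit in Epic while pregnant").

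Section 3.1.1 restricts candidate confounders and gives the reason: "Only baseline variables will be evaluated as potential confounders, as they could not have been affected by use of the app". It also says: "We will report the results of two models for each outcome". The first of the two is limited to confounders drawn from the literature, and the second adds those found empirically. Hospital is in none of the literature lists in Sections 3.1.1 and 3.1.2.

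For the propensity score, Section 3.1.5 says: "Baseline confounders will be included in the propensity score model, if they are related to the likelihood of receiving treatment and the outcome". It excludes first-visit date by name and does not mention hospital. On calendar time, "we will conduct a sensitivity analysis including a time effect". There is no corresponding analysis that removes hospital.

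**The concern.** The app is prescribed at an early prenatal visit. Delivery hospital is settled at birth, together with gestational age. The one covariate required in every model therefore fails, by timing, the condition the SAP gives for admitting a covariate.

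The path that matters most does not run through the app. If early or complicated births tend to be delivered at a particular hospital, delivery hospital is partly a consequence of the outcome. If the cohorts also use that hospital to different extents, conditioning on it shifts the cohort contrast. The primary outcome and preterm birth (secondary outcome 1) are the most directly exposed.

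No planned analysis clearly shows the effect. Under the all-models rule, both models per outcome contain hospital. The time-effect analysis adds a covariate and does not say that hospital is removed. The descriptive cohort means in Section 2.6 omit hospital, but they omit every other confounder too. The literature-only model might have been meant to omit hospital, but then two statements in Section 3.1.1 contradict each other.

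**Working it through.** **The plan's own figure.** With cohorts of 7147 and 5197 and SD 10 days (Section 1.5), SE = 10 × √(1/7147 + 1/5197) = 0.182 days. The detectable difference at two-sided 5% and 80% power is (1.960 + 0.842) × 0.182 = 0.51 days, as stated. That figure is not in dispute and serves as the yardstick.

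**Assumed inputs.** The SAP gives neither routing nor hospital mix, so everything below is illustrative:
- Two hospitals, no true app effect, no true hospital effect. The referral hospital is the first-visit site for 35% overall.
- Births below 259 days at the other site move to the referral hospital with probability (target share − 0.35)/0.65.
- Mild routing has target shares of 45% at 34–36 weeks and 68% below 34 weeks, giving probabilities 0.154 and 0.508.
- Steep routing has target shares of 65% and 90%, giving 0.462 and 0.846.
- Three gestational-age distributions: normal(275, 10); 0.95 normal(276.3, 8) + 0.05 normal(256, 18); 0.95 normal(276.3, 8) + 0.05 normal(253, 20). SDs are 9.8 to 10.3 days and the preterm share is 4.0% to 4.9%.
- No covariate other than hospital is modelled.

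**Formula.** Adjusted estimate = crude estimate − γ × δ, where δ is the cohort gap in delivery-hospital share and γ is the within-cohort least-squares slope of the outcome on delivery hospital. Here the crude estimate is zero, so the bias is −γδ.

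**One cell in full** (normal distribution, steep routing, 10-point gap). The share moved from the other site is about 0.462 × 0.0494 = 0.0228, so δ = 0.10 × (1 − 0.0228) = 0.0977. Least squares gives γ = −1.34 days, so the bias is 1.34 × 0.0977 = 0.131 days. For preterm birth γ = 6.15 points, so the bias is −6.15 × 0.0977 = −0.60 points.

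**All cells** (absolute bias, range over the three distributions):

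| Cohort gap | Days, mild | Days, steep | Preterm points, mild | Preterm points, steep |
|---|---|---|---|---|
| 0 | 0 | 0 | 0 | 0 |
| 2 points | 0.009–0.022 | 0.026–0.044 | 0.04–0.06 | 0.11–0.13 |
| 5 points | 0.022–0.055 | 0.065–0.11 | 0.10–0.14 | 0.28–0.31 |
| 10 points | 0.045–0.11 | 0.13–0.22 | 0.21–0.28 | 0.57–0.63 |

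(The 2-point preterm entries are 2/5 of the 5-point entries, since bias is nearly proportional to the gap.) Without routing, every entry is zero. The bias favours whichever cohort uses the referral hospital more: its gestation looks longer and its preterm rate lower.

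**Against the standard errors.**
- Gestational age: at a 5-point gap the largest bias is 0.11/0.182 = 0.6 SE. At 10 points with steep routing it is 0.7 to 1.2 SE.
- Preterm birth: the unadjusted SE is 100 × √[p(1−p)(1/7147 + 1/5197)], or 0.36 to 0.40 points for p = 4.0% to 4.9%. The 10-point steep cell is then about 1.5 to 1.7 SE.

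**App-mediated path alone.** With a 0.5-day app effect and no cohort gap, adjusting for delivery hospital dilutes the effect by about 0% to 2%.

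**If hospitals truly differ** (10-point gap, gestation shorter at the referral site; bias in days):

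| True site difference | Omitting hospital | Adjusting, mild | Adjusting, steep |
|---|---|---|---|
| 1 day | −0.10 | +0.04 to +0.11 | +0.13 to +0.22 |
| 2 days | −0.20 | +0.04 to +0.11 | +0.12 to +0.21 |

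**The case against.** The strongest defence is that the harm needs two facts the SAP does not supply, and is zero if either is absent. For many participants the delivery hospital may simply be their usual site, which suits the stated purpose of the adjustment. That stands: bias here is possible, not shown.

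Second, adjusting can be the better choice. With a 2-day site difference, the adjusted bias is below the unadjusted 0.20 days in five of six cells and about equal in the sixth. Adjusting does worse mainly when routing is steep and true site differences are small. That also stands.

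Third, the label is loose across Appendix A. Age, height and the payor fields are also dated to delivery yet typed as baseline, and insurance type is a listed confounder. This is fair, and HOSPITAL is not a lone mislabelling. But gestational age scarcely moves age or height, whereas place of birth can depend directly on how early or complicated the birth is. Hospital is also the covariate the plan requires in all models.

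Fourth, comparing models with and without hospital cannot show which is biased. At a 10-point gap the two estimates differ by 0.24 to 0.31 days for a 2-day site effect with mild routing, and by 0.23 to 0.32 days for a 1-day effect with steep routing. These cannot be told apart. The pair shows sensitivity and no more.

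A reader might infer that the app itself distorts the estimate by changing where people deliver, or that hospital should be dropped. Neither follows. The app path is worth at most about 2% dilution under these assumptions, and omitting site has its own bias when hospitals differ.

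**Conclusion.** The inconsistency in the text holds whatever its size. A variable fixed at delivery is labelled baseline and required in all models, against the SAP's stated reason for using baseline variables only. The literature-only model and the all-models rule also disagree. Whether that rule reaches the propensity and weighting models is not stated.

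The statistical consequence is conditional. If delivery hospital depends on gestational age or complications, and hospital mix differs between cohorts, adjustment can bias the two gestational outcomes. Under the assumed inputs this is mostly below one standard error for gestational age. It reaches about 0.2 days and 0.6 percentage points of preterm birth only with steep routing and a 10-point gap. The document does not support the stronger reading that the planned primary estimate is biased. This is a minor to moderate point, worth correcting because the correction is cheap.

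**What to change.** 1. In Appendix A, relabel HOSPITAL as recorded at delivery.
2. If the EHR holds the site of the first prenatal or prescribing visit, use that as the site covariate in the outcome, propensity and weighting models, with delivery hospital as a sensitivity analysis. Appendix A lists only the date of that visit, so availability must be checked.
3. If it does not, keep the model with HOSPITAL as the named primary, and pre-specify a sensitivity model without it for gestational age and preterm birth.
4. Reconcile the two statements in Section 3.1.1 by saying whether the literature-only model contains hospital. State in Section 3.1.5 whether the all-models rule covers the propensity and weighting models.
5. Report any with/without pair as showing sensitivity to hospital adjustment, not as identifying the unbiased estimate.

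The cost is some SAP wording, one extra set of models for two outcomes, and possibly one extra EHR field. It is best settled before the cohort labels are unblinded.

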1.5. Sample Size Justification

Due to the observational nature of the study and recruitment context, it was not possible to predetermine the sample size based on statistical power for estimating the primary and secondary outcomes. Instead, all participants who met the inclusion criteria between September 2019 and February 2022 were included. The final sample has 12,344 deliveries, divided between the MHP and usual care cohorts (with 7147 in one and 5197 in the other, with their identities currently blinded). This represents about 12,287 different participants (we only have information about the percent of multiple deliveries for participants who downloaded the app, 0.464%). Given the sample sizes in the two cohorts, there is 80% power to detect an effect size of 0.051 days. Assuming that the outcomes are normally distributed with a standard deviation of 10 days (1), the study has 80% power to detect a 0.51 day difference in gestational age at birth between the cohorts.

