3.1. Main analyses of treatment differences

The main analysis compares the mean gestational weeks at birth between the MHP and usual care cohorts. An estimate of the average treatment effect, 95% confidence interval, and effect size will be reported. EG will remain blind to the 80% of outcome data not used to set the terms of the analysis (Section 2.5).

The primary and secondary outcomes will be evaluated at the 5% significance level. No correction for chance will be used for the primary outcome, as there is only one test. For the 9 secondary outcomes, we will report both corrected and uncorrected p-values, using the Bonferroni correction to reduce risk of reporting a false positive result. As a sensitivity analysis, the Bonferroni corrected p-values for ten outcome values will be reported in the supplemental material of the report.

All tests will include all participants with data on the outcome measure involved.

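### Calendar time is left out of the outcome models and the propensity score because the app's effect may vary with it, which is not a reason to omit a possible confounder

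*SAP*

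**What the plan says.** SAP section 3.1.1 names the date of the first recorded visit as a covariate specific to this dataset and says it may reflect access to care and social conditions, with the pandemic as its example. It then excludes it: "We will not include date of first visit as it might be correlated with ones that affect the effectiveness of the app over time". Section 3.1.2 applies the primary-outcome procedures to the secondary outcomes, so the exclusion carries over to them.

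Section 3.1.5 repeats the exclusion for the propensity score: "Date of first visit will not be included in the model (for reasons given in Section 3.1.1". Under its time-effects heading it accepts that "During the study time frame, many outside factors could have affected the outcomes, especially due to the COVID-19 pandemic", and responds that "we will conduct a sensitivity analysis including a time effect, the date of the participant's first prenatal visit, in each model".

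Two other provisions bear on this. Section 3.1.1 sends baseline variables with inconclusive evidence to a 10% change-in-estimate test, and it puts hospital location in every model. Appendix A lists the date (PREG_CONTACT_DATE) as a baseline covariate.

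**The concern.** A variable that changes how well the app works is an effect modifier. A variable related to both downloading and the outcome is a confounder. The same variable can be both, and being the first is no ground for ignoring the second. A main effect of a pre-exposure date removes differences in when the two cohorts were pregnant; it does not remove the app effect.

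The SAP's handling is also uneven. Hospital location is forced in because it may reflect resources, practices and populations, any of which could equally alter the app's effect. Date, described in similar terms, is ruled out before the SAP's own 10% test can be applied.

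At stake is whether a difference in calendar mix is read as an app effect. With 12,344 deliveries the standard error is small, so a modest systematic difference can reach significance. Matching and weighting would not detect it: date is excluded from the propensity score, and no second propensity model is described for the weighting. The literature-only models for referrals and appointment attendance are the most exposed, because section 3.1.2 identifies no confounders for those four outcomes, which leaves only hospital location.

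**Working it through.** **Inputs from the SAP.** Cohorts: "with 7147 in one and 5197 in the other, with their identities currently blinded" (section 1.5). Outcome spread: "Assuming that the outcomes are normally distributed with a standard deviation of 10 days" (section 1.5). Test level: "The primary and secondary outcomes will be evaluated at the 5% significance level" (section 3.1), taken as two-sided because that reproduces the stated power.

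**The plan's own figure.**
- SE = 10 × √(1/7147 + 1/5197) = 0.182 day.
- Detectable difference at 80% power = (1.960 + 0.842) × 0.182 = 0.51 day, as stated in section 1.5.

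**Assumptions, because the SAP gives no uptake or outcome by date.** Two equal halves of the sample, an uptake change of d between them, an outcome shift of s days, and an overall cohort share p = 7147/12,344 = 0.579. Using 0.421 gives the same results.

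**Bias if time is omitted.**
- Imbalance between cohorts in the later-half share = d / [4p(1 − p)] = d / 0.975.
- Bias = imbalance × s. False-positive rate = P(|Z + bias/SE| > 1.96).
- For d = 0.20 and s = 1: 0.20/0.975 = 0.205, so the bias is 0.21 day, or 1.13 SE, and the false-positive rate is 20.3%.

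| Uptake change | Outcome shift (days) | Bias (days) | False-positive rate |
|---|---|---|---|
| 5 points | 0.25 | 0.01 | 5.1% |
| 5 points | 1 | 0.05 | 5.9% |
| 10 points | 1 | 0.10 | 8.7% |
| 20 points | 1 | 0.21 | 20.3% |
| 30 points | 1 | 0.31 | 39.3% |
| 30 points | 2 | 0.62 | 92% |

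A simulation of the 20-point, 1-day case with no true effect (2000 runs) gave a mean estimate of 0.21 day and 21.6% rejections without time. With a period term it gave 0.00 day and 5.2%.

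**Testing the SAP's reason.** In a second simulation the app effect itself varied by period (0.25 and 0.75 day, average 0.50), with the same 20-point and 1-day drifts. Without time the estimate was 0.75 day; with a main effect of time it was 0.48 day. Adjustment stayed near the average effect even though effectiveness changed, and omission did not.

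**What one linear date term would remove.** Take dates uniform over a window of length 1, with the step at the midpoint. The remaining bias is d·s·(1/48 − 1/64) / [p(1 − p)/12 − d²/64].
- 70% then 46% uptake, 1 day: 0.24 × 0.00521 / (0.0203 − 0.0009) = 0.06 day, down from 0.25. The false-positive rate falls from 27% to 6.4%.
- 75% then 41%, 1.5 days: 0.51 × 0.00521 / (0.0203 − 0.0018) = 0.14 day, down from 0.52. The rate falls from 82% to 12%.

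For a rise and fall, let the two equal groups be the middle half of the window and its two outer quarters. By symmetry neither uptake nor outcome is then correlated with a linear date. The linear term removes nothing, and the 20-point, 1-day case keeps its full 0.21 day.

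**The case against.** The strongest reply is that the SAP already prespecifies a time-adjusted analysis of each model, so any calendar effect would be visible and the argument is only about which model carries the primary label. Much of this stands. For a one-way step, even a linear date term removes about three quarters of the bias, as shown above.

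Three gaps remain. The sensitivity analysis does not decide the result, and no rule says what follows if it disagrees with the primary model. Its functional form is not fixed, so a linear term is possible and could miss seasonal or wave-shaped change. It is also unclear whether the time effect extends to the propensity model, from which the same section excludes date.

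A reader might infer that every deciding comparison is confounded. The SAP does not support that: confounding needs drift in both uptake and outcome, and neither is reported. Both cohorts were prescribed the app, so changes in prescribing matter only if they changed the download share.

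A reader might also point to the November 2020 change in what the app logged (Appendix A). That affects usage metrics for the dose-response analysis. It does not affect cohort membership, which is defined by download, or the EHR outcomes.

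**Conclusion.** The point holds as a weakness in the choice of primary model and propensity score. The stated reason for excluding date is effect modification and does not justify the omission. The SAP's own description makes date a candidate confounder.

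Whether the deciding estimates are actually biased cannot be told from the SAP. Under the assumed drifts the bias ranges from negligible (0.01 day) to above the 0.51-day detectable difference (0.62 day), with 0.21 day and a 20% false-positive rate at a 20-point uptake change and a 1-day shift. These figures rest on an SD of 10 days, two equal periods and no adjustment for other covariates. The planned sensitivity analysis lessens the problem but does not close it. The change should be made because it is cheap and protects the primary result.

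**What to change.** In sections 3.1.1, 3.1.2 and 3.1.5:

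- Include calendar time in the primary and secondary outcome models and in the propensity score used for matching and weighting. Use calendar-month categories or a spline of PREG_CONTACT_DATE. Alternatively use the estimated start of pregnancy, PREG_CONTACT_DATE minus GESTAGE_ATVISIT_DAYS, which separates calendar time from late entry to care. First confirm that both variables refer to the same visit, since Appendix A does not say that the gestational age is from the first one.
- Make the model without calendar time the sensitivity analysis.
- If changing effectiveness is of interest, examine it with a separate cohort-by-period interaction.

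The cost is SAP wording and some extra terms: about 30 for monthly categories, fewer for a spline. With 12,344 deliveries the loss of precision is negligible, and both variables are already listed in Appendix A.
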